**Table 5: ROIs for Fixed Anatomical Structure (i.e., Critical Network Nodes for Most Cognitive Skills)**

Networks	Network Nodes/Regions of Interest (ROI)
VAN-Salience	1. right ventral frontal cortex/anterior insula (R VFC/AI) 2. right temporal-parietal junction (R TPJ)
DAN	3. right frontal eye fields (FEF) 4. left FEF 5. right intraparietal sulcus (IPS) 6. left IPS
DMN	7. medial prefrontal cortex (mPFC) 8. posterior cingulate cortex (PCC) (also in FPCN)
FPCN or ECN	9. Left dorsolateral prefrontal cortex (DLPFC) 10. Right DLPFC 11. Parietal association region (PAR) 12. Posterior cuneus (pCUN)

**VAN** = Ventral Attention Network; including salience network; **DAN** = Dorsal Attention Network; **DMN** = Default Mode Network; **FPCN or ECN** = Frontal Parietal Cortical Network also referred to as the Executive Control Network

After the group model has been developed it is used as a fixed component in the determination of each individual's model that then delineate sub-types/subgroups of persons sharing a common (75% threshold) ROI structure.

The goal is to identify the optimal GIMME brain region (ROI) for stimulating with iTBS. To identify this ROI, we will first identify the best representative pathway (e.g., a pathway is comprised of two ROIs).

To identify the best representative pathway, we will first identify a pathway from each model level (group, sub-types and individual) by using the average the betas (mean betas,  $\mu\beta$ ), for all of the group-level pathways subgroup-level pathways, and individual pathways for each person comprising each model. From all the  $\mu\beta$  weights from each model level, we will select the pathway with the maximum  $\mu\beta$  weight. Now that the pathway-level (group, subgroup or individual) has been selected, the path within this collection having the max  $\beta$  weight will be selected as the pathway most important to cognitive function for this specific participant.

Since we seek to identify one ROI as the optimal iTBS GIMME target and as each pathway is comprised of two ROIs, we will select one of the two ROIs comprising the pathway selected as the most important to cognitive function. This ROI is the ROI with the highest total degree. The graph theory metric of total degree quantifies the sum of in-degree (number of connections coming into the ROI) and out degree (outbound connections). As both in and out degree reflect importance of the ROI to cognition, we will use total degree to select the optimal brain region. If the total degree between the brain regions is equal, we will base the decision on TMS accessibility, Gray Matter Density and/or structural integrity.

Regarding testing Aim 4, the results from above GIMME modeling and decision criteria will, ultimately, test hypothesis that, within our study population of persons **with** moderate cognitive impairment from TBI, there are sub-types/sub-groups of persons with common brain circuitry important to cognition.

Past GIMME work indicates that a minimum of 7 persons with moderate cognitive impairment from TBI will be sufficient to identify an optimal group-level model as well as sub-types/subgroups. That is, 7 participants per diagnosis, here moderate cognitive impairment from TBI, has consistently identified an optimal group-level model as well as subgroups within this diagnosis. Thus, we will strive to enroll at least 7 participants into these optional studies.

**AIM 5:** Determine immediate gains in working memory and performance of complex IADL after provision of a single session of iTBS targeting to the same location in the L DLPFC after a single session of iTBS targeting the optimal GIMME brain target. We hypothesize that average gains in working memory and functional performance after a single iTBS session site will be

significantly different according to site of stimulation (GIMME site). For each iTBS session, we will compute pre and post iTBS MDS and AMPS scores to be used to compute change in working memory and functional performance of IADL. For each outcome and each treatment site, the mean change will be computed. Using student t-tests, we will compare mean change in working memory and mean change in functional performance between the L DLPFC vs GIMME sites. This will allow us to examine the concept that treatment sites personalized by ROI structure is or is not important for optimizing clinical benefits of iTBS.

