**Additional exploratory aims are:**

**Aim 4:** Optimal Neural Targets for iTBS using Group Iterative Multiple Model Estimation (GIMME) based on *ab a priori* fixed network structure comprised of 12 anatomical nodes associated with cognitive processing. GIMME will be used to identify common, subgroup and unique neural circuits of moderately cognitively impaired participants. For persons with moderate cognitive impairment resulting from TBI, we hypothesize that there will be sub-types of persons with common brain circuitry important to cognition.

**Aim 5:** Determine immediate gains in working memory and performance of complex IADL after provision of a single session of iTBS targeting to the same location in the L DLPFC that was treated and after a single session of iTBS targeting the optimal GIMME brain target. For persons with moderate cognitive impairment resulting from TBI, we hypothesize that average gains in working memory and functional performance after a single iTBS session site will be

significantly different according to site of stimulation (L DLPFC site, GIMME site).

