**Study-Day 4 (2 weeks after Study-Day 3) (~2.5 hours):**

[figure not shown]
- 1. PE testing battery
- 2. Suitability rating 1-8

**Optional Study for Participants with diagnosis of TBI only- Day 5 (to occur within 2 weeks of Day 4, can occur on same day as Day 4) (~2 hours)**

- 1. Single session of Active iTBS at GIMME site of stimulation
- 2. ImE test: MDS, one time only
- 3. ImE test: AMPS, one time only

### Figure 3. Study Procedures by Study-Days 1 thru 4

ImE = Immediate Effects Tests; s-AMPS = Streamlined AMPS or MDS = Modified Digit Span; PE = Persisting Effects Tests for all participants

**Interventions.** All iTBS sessions will be **double-blinded**, but APT exercises **will not be blinded**. For **Active** iTBS and **Placebo** iTBS, the left DLPFC using the Resting Network Mapping algorithm.

**fMRI (neuroimaging)-** Functional MRI (fMRI) measures will be collected at Baseline. The fMRI measures will include structural imaging, 20 minutes of resting-state fMRI, diffusion tensor imaging (DTI) and an Arterial Spin Labelling Sequence (ASL). Participants will be in the MRI for approximately 55 minutes. fMRI scanning, for all participants, will take place at Northwestern University's CTI in the Olsen Pavilion located at [name].

Veterans will be responsible for transportation to the CTI, however parking vouchers will be provided at no cost to the participant. Parking is available at the Northwestern Memorial Hospital parking garage located across from the Olsen Pavilion. Research staff will be present on day of scan and available to provide assistance.

Scanning will take place on a Siemens Prisma 3.0 T MRI scanner equipped with a 64-channel head/neck coil. A high-resolution 3D MP-RAGE T1-weighted sagittal anatomical scan (voxel size = 0.8 mm isotropic resolution; 224 sagittal slices) will be collected for each participant. Resting state BOLD data will be collected using T2\* weighted EPI with a TR=0.5s, TE=25ms, flip angle of 48°, and 2mm isotropic voxels and a multiband factor of 8. Rest data will be collected while the subject views a fixation crosshair. The DTI data will use a two shell (64 directions per shell) acquisition with diffusion values of 1000 mm^2/sec. The acquisition will collect 1.5mm isotropic voxels with a TR=4500, TE=62ms and a multiband factor of 4, and 96 slices.

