For Aim 4 we will identify the optimal iTBS Neural Targets using GIMME, which is a directed functional connectivity modeling approach based on iterative model optimization. The optimal brain target is the region that, when modulated, communicates effectively with the neural systems supporting cognition such that it leads to improved cognitive abilities. This target could be a brain region defined at the group level (i.e., generalizable to mild TBI+PTSD population), the subgroup level (specific to mild TBI+PTSD persons with shared features), or at the individual level. GIMME is based on a feed forward method of adding paths among the pre-specified brain Regions of Interest (ROIs) that serve as a fixed anatomical structure. Considering that GIMME models have included 7 to 20 ROIs, the fixed GIMME anatomical structure will include a set of 12 ROIs implicated in cognition and that serve as nodes in neural networks based on a parcellation atlas will be used in all GIMME models to as the fixed anatomical structure. (Table 5). The threshold for a group-level or sub-group-level pathway connection can be manipulated but we will use 75% as it has been determined to work well. Based on the fixed anatomical structure, GIMME first produces a group-level model of the ROI structure common to at least 75% of the persons in the full dataset/sample.

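### Aim 4 is said to test that TBI sub-types with cognition-relevant circuitry exist, but its procedure uses no cognitive score and allows no result that would refute the hypothesis

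*Combined protocol and SAP*

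**What the plan says.** 3.0 Objectives lists Aim 4 under "Additional exploratory aims are". For moderate cognitive impairment from TBI it states: "we hypothesize that there will be sub-types of persons with common brain circuitry important to cognition".

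5.6 Data Analysis gives the procedure.

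- GIMME is fitted to "a set of 12 ROIs implicated in cognition" (Table 5), first at group level. On the threshold for group and subgroup paths the plan says "we will use 75% as it has been determined to work well".
- The group model is then held fixed, individual models are built on it, and persons who share structure at the same threshold form subgroups.
- To choose a target, betas are averaged at each level (group, subgroup, individual) and the level with the largest mean is taken. The path with the largest beta within that level "will be selected as the pathway most important to cognitive function for this specific participant".
- Of that path's two regions, the one with the higher total degree becomes the target. TMS accessibility and structural measures only break ties.

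On inference, 5.6 says that "the results from above GIMME modeling and decision criteria will, ultimately, test hypothesis that, within our study population", there are sub-types with common circuitry important to cognition. The minimum of 7 participants is justified because that number "has consistently identified an optimal group-level model as well as subgroups within this diagnosis". The false discovery rate paragraph is introduced for Aims 2 and 3. Aim 5 compares mean MDS and AMPS change between the left DLPFC site and the GIMME site by t-test.

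**The concern.** Aim 4 makes two claims: that sub-types exist, and that the circuitry they share matters to cognition. A test of the first needs some way to distinguish a sample with sub-types from one without. A test of the second needs a measure of cognition. The procedure has neither. If it is followed exactly, any subgroups returned can be reported as support for the hypothesis, and the strongest path can be reported as the one that matters to a Veteran's cognition, with no evidence behind either statement. The targets chosen under that label then go into Aim 5.

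**Working it through.** **Step 1. What enters the procedure.** From 5.6, Table 5 and the imaging description in 5.1:

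| Step | Input | Cognitive score used? |
|---|---|---|
| Choice of 12 regions | prior knowledge and an atlas | no |
| Group model | regional time series, 75% threshold | no |
| Individual models and subgroups | same series, 75% threshold | no |
| Path choice | largest mean beta, then largest beta | no |
| Region choice | total degree; ties by accessibility or structure | no |

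RBANS, Digit Span, DKEFS, MDS and AMPS appear in none of these steps. The plan does not name the GIMME input outright. Resting-state fMRI is taken as the input because, apart from a perfusion (ASL) sequence, it is the only functional acquisition listed and no task fMRI is planned.

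**Step 2. What would refute the hypothesis.** No statistic, no-subgroup reference, minimum subgroup size, stability check or failing result is given. The clustering algorithm is not named.

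**Step 3. Whether Aim 5 fills the gap.** The target may come from the group, subgroup or individual level. A site difference can therefore appear without sub-types, and sub-types can exist without a site difference.

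**Step 4. How often subgroups appear when there are none.** The plan's figure of 7 rests on a cited source and carries no error rate, so it cannot be reproduced by a formula. The calculations below use path presence or absence, not full GIMME fits. Path prevalence q, detection rates, minimum subgroup size and clustering method are assumptions.

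Inputs from the plan: 12 × 11 = 132 directed paths (lagged paths not counted); n = 7 (minimum), 12 (optional-study maximum) or 24 (all TBI participants), since the plan does not say which scans are modelled. The 75% group threshold is ceil(0.75n) = 6, 9 and 18 persons.

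(a) *Rule as worded, independent personal paths.* The chance that at least one path is shared by k or more persons but falls below the group threshold is

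1 − (1 − P(k ≤ X ≤ ceil(0.75n) − 1))^132, with X ~ Binomial(n, q).

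Example, n = 7, q = 0.05, k = 3: P = 0.00356 + 0.00019 + 0.00001 = 0.00376, and 1 − (1 − 0.00376)^132 = 0.39.

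| | q = 0.02 | 0.05 | 0.10 | 0.15 |
|---|---|---|---|---|
| n = 7, k = 3 | 0.03 | 0.39 | 0.97 | 1.00 |
| n = 7, k = 4 | 0.00 | 0.03 | 0.30 | 0.80 |
| n = 12, k = 3 | 0.18 | 0.93 | 1.00 | 1.00 |
| n = 24, k = 3 | 0.79 | 1.00 | 1.00 | 1.00 |

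(b) *With a clustering step* (random-walk/modularity type on shared-path counts, 1,000 samples per setting). A false subgroup is a cluster with a non-group path shared by at least 75% of its members.

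| No-subgroup model | Minimum size | n = 7 | n = 12 | n = 24 |
|---|---|---|---|---|
| Independent personal paths, q = 0.02 to 0.30 | 2 | 0.36–0.59 | 0.55–0.76 | 0.40–0.82 |
| Same | 3 | 0.03–0.45 | 0.11–0.66 | 0.26–0.80 |
| Same 25 paths for all, detected with probability 0.70–0.95, false paths at 0.01–0.05 | 3 | 0.02–0.14 | 0.00–0.23 | 0.00–0.44 |

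(c) *Definition alone.* In a further simulation at n = 7 with 3, 5 or 10 random extra paths per person, modularity maximisation returned two or more multi-person subgroups in about 33%, 84% and 100% of samples. Requiring three or more members with a 75%-shared path cut this to 7–47%.

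**Step 5. Whether a calibrated test is workable.** Modularity was compared with a permutation reference (99 permutations, p ≤ 0.05, q = 0.15; 100 samples at n = 7 and 12, 30 at n = 24). False positives were about 10%, 3% and 7%. With 100 samples the standard error around 5% is √(0.05 × 0.95/100) = 2.2 points, so the 10% at n = 7 is somewhat high and the run is too small to settle it. Power for two planted subgroups, each with 5 own paths present in 80% of members, was about 26%, 71% and 97% at n = 7, 12 and 24.

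**The case against.** The aim is exploratory and claims no alpha, so holding it to a 5% error rate applies a standard it did not adopt. The regions were pre-selected for their role in cognition, and every participant was selected on cognitive tests. The wording about the most important pathway names a target-selection rule, not a reported test. Aim 5 checks with MDS and AMPS whether personalised sites help. The simulations do not run GIMME on time series.

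Much of this stands. The exploratory label lowers the stakes, Aim 5 is a real check on targets, and the simulated rates show sensitivity to assumptions rather than this plan's behaviour. None of it supplies the missing test. The plan says that the output will test a stated hypothesis, and an exploratory label does not turn a description into a test. Pre-selecting regions makes every path among them equally eligible, so it cannot show which path matters to whom. Selecting impaired participants restricts the range of cognition; it does not link cognition to a path.

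**Conclusion.** The concern holds in this form: Aim 4 describes sub-types; it does not test whether they exist or whether their circuitry matters to cognition. The false-subgroup rate is uncontrolled and can be high. It runs from near 0 to near 100% with path prevalence, minimum subgroup size, clustering method and no-subgroup model, none of which the plan fixes. No single figure should be quoted.

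A reader might infer more than the documents support:

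- *That most samples without sub-types would yield them, or that Aim 4 will very probably be reported as confirmed.* This fails in many clustered settings, and in every clustered setting where all persons share one network (at most 0.44 for three or more persons).
- *That past consistency at 7 participants makes a finding weak evidence.* This depends on whether the cited samples truly contained subgroups, which the documents do not show.
- *That the error passes into the biotype algorithm.* The Abstract and 3.0 mention that algorithm only as future work and do not say it will use GIMME sub-types.

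The point should be corrected before Aim 4 is analysed. It does not bear on Aims 1 to 3.

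**What to change.** In 5.6, Aim 4:

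1. State that GIMME sub-types will be reported as descriptive. Claim that they exist only if the observed modularity exceeds the 95th percentile from rerunning the same subgrouping on data generated without subgroups. Fix the clustering algorithm, the minimum subgroup size and the set of TBI scans to be modelled in advance.
2. Replace the wording that calls circuitry or a path important to cognition, here and in the Aim 4 hypothesis in 3.0, with: strongest resting-state path among the pre-selected ROIs.

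Correlating the selected path's beta with RBANS or Digit Span would not earn the stronger label. The path differs between participants, so the pooled association is ill-defined, and the 95% interval around r = 0 is tanh(±1.96/√(n − 3)), about ±0.75 at n = 7 and ±0.57 at n = 12.

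The cost is wording and computing time; no new data are needed. The downside is low power at the plan's minimum: with about 26% at n = 7 in the illustrative run, Aim 4 will probably be descriptive only unless more scans are modelled.

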**Study-Day 1 (~5 hours) (may occur over 2 days):**

- 1. Complete tests/questionnaires that are not repeated. Some are collected for use as covariates (Table 2) and some are needed for treatment preparation.
  - a. Baseline testing battery
  - b. APT Baseline
  - c. fMRI-to be completed at NU CTI
  - d. Motor Threshold
  - e. Baseline EEG\*
- 2. Rating suitability of the number and types of tests 1-3.

\*EEG to be completed prior and reviewed by physician prior to Motor Threshold

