**Study-Day 2 (4 days after Study Day 1)(~8 hours):**

- 1. PE testing battery
- 2. A single session of **Active** iTBS or **Placebo** iTBS
- 3. Randomly assigned ImE test (MDS or AMPS), administered 3-times at 30 min intervals, each interval includes 5 to 15 min of rest).
- 4. PE testing battery
- 5. Suitability ratings 1-3

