**Study-Day 3 (2 weeks after Study Day 2)(~8 hours):**

- 1. PE testing battery
- 2. Single session **Active** iTBS+ APT or **Placebo** iTBS+APT
- 3. Alternate ImE test (MDS or AMPS) three times at 30min intervals
- 4. PE testing battery
- 5. Suitability ratings 1-3

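### Aim 5 (exploratory) needs an MDS score before and after each iTBS session, but the schedule lists MDS only after stimulation, and the L DLPFC side is tied to no session or treatment arm

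*Combined protocol and SAP*

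**What the plan says.** Section 5.6 (Aim 5) gives the outcome rule: "For each iTBS session, we will compute pre and post iTBS MDS and AMPS scores to be used to compute change in working memory". The test follows: "Using student t-tests, we will compare mean change in working memory and mean change in functional performance between the L DLPFC vs GIMME sites". It does not say whether the t-test is paired. Section 3.0 identifies the comparator only by location, as the L DLPFC site already treated, with no study day.

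The schedule is in Section 5.1:

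- **Study-Day 1:** an entry reading "Baseline testing battery", not itemised.
- **Study-Day 2:** persisting-effects (PE) battery, then iTBS, then "Randomly assigned ImE test (MDS or AMPS), administered 3-times at 30 min intervals", then the PE battery again.
- **Study-Day 3:** the same order with iTBS + APT, then "Alternate ImE test (MDS or AMPS) three times at 30min intervals".
- **Study-Day 4:** PE battery (B4).
- **Optional Day 5:** on the same day as Day 4 or up to 2 weeks later. It opens with "Single session of Active iTBS at GIMME site of stimulation", followed by "ImE test: MDS, one time only" and one AMPS.

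Section 5.5 puts AMPS and WAIS-IV Digit Span in the PE battery. Table 2 lists MDS only as an immediate-effects (ImE) test, with 3 repetitions, for Aims 1 and 2.

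Optional entry (Sections 3.0 and 5.4) is for up to 12 TBI Veterans who completed the main study, whatever their arm. The lower target is in Section 5.6: "Thus, we will strive to enroll at least 7 participants into these optional studies". The iTBS description in Section 5.1 says that the Placebo arm gets no stimulation.

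**The concern.** A pre-to-post change needs a score on each side of the stimulation. If the schedule holds no MDS before stimulation, the working-memory half of Aim 5 has no data in the form the plan defines, and a missing pre-score cannot be recovered once the session has passed.

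Two further gaps affect what can be compared. For AMPS there are several candidate scores and no rule for choosing among them. For the L DLPFC side, the text does not exclude Veterans whose only L DLPFC sessions were placebo. The number of Veterans with usable data at both sites may therefore be well below the 7 to 12 planned joiners.

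**Working it through.** **Step 1. Reproduce the plan's MDS count.** Each Veteran has MDS on Day 2 or Day 3, three times. That gives 3, which matches Table 2. Day 5 adds 1, so 3 + 1 = 4 of the 6 forms.

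**Step 2. Place each administration relative to stimulation.**

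| Visit | MDS before | MDS after | AMPS before |
|---|---|---|---|
| Day 2 or 3 (the MDS day) | 0 | 3 | 1 (PE battery) |
| Day 5 | 0 | 1 | none listed; nearest is B4 |

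The MDS result is the same in both ImE orders. The 3 repetitions in Table 2 are used up by the post-stimulation series, so no MDS is left to serve as a pre-score.

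**Step 3. AMPS.** Days 2 and 3 have a same-day pre-score. For Day 5 the nearest is B4, which is same-day only if Days 4 and 5 coincide and is otherwise up to 2 weeks old. Candidate post-scores on Day 2 are any of the three ImE administrations or B1. B1 comes after the whole ImE series: 3 × 0.2 h = 0.6 h of MDS or 3 × 1.5 h = 4.5 h of AMPS (Table 2 times), plus rest.

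**Step 4. Veterans with an active L DLPFC session.** Inputs from Section 5.1: 24 TBI Veterans, half Active, so 12. Assumptions: Day 5 as listed is the whole optional schedule, and joining is unrelated to arm. The expected number among n joiners is n × K / 24 (hypergeometric).

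- Active arm, K = 12: 12 × 12/24 = 6.0 of 12 (central 95% range 4 to 8); 7 × 12/24 = 3.5 of 7 (1 to 6).
- Active arm with MDS on Day 2, K = 6 (assumed 6/12 split): 12 × 6/24 = 3.0 of 12 (1 to 5); 7 × 6/24 = 1.75 of 7 (0 to 4). With 7 joiners the chance of at most one such Veteran is 0.41.
- The Day 2 split within Active TBI Veterans is not stated. For K = 4 to 8 the expected counts are 2.0 to 4.0 of 12, or 1.2 to 2.3 of 7.
- The same 6/12 split gives the same expected counts for AMPS as the Day 2 ImE test.

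**Step 5. Precision.** The 95% CI half-width for a paired mean difference, in SDs of the difference, is t(0.975, n−1)/√n:

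- n = 3: 4.303/1.732 = 2.48
- n = 6: 2.571/2.449 = 1.05
- n = 7: 2.447/2.646 = 0.92
- n = 12: 2.201/3.464 = 0.64

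**Step 6. The other reading.** Sections 3.0 and 5.3 speak of optional sessions in the plural, and Aim 5 in Section 3.0 could mean a further L DLPFC session. All 7 to 12 joiners would then have both sites (half-width 0.92 to 0.64 SD). The listed Day 5 MDS would still come only after stimulation.

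**The case against.** **A baseline may be implied or out of sight.** Digit Span is the parent test of MDS, is scored as percent correct in Table 2, and is given before iTBS on Days 2 and 3. Figures 2 and 3 are not shown, and the Day 1 battery is not itemised. This limits certainty but does not remove the mismatch. Section 5.6 names MDS, not Digit Span; Day 5 lists neither before stimulation; and a Day 1 MDS would not be a pre-score for each session.

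**The comparator can be inferred.** Day 2 is the only iTBS-alone session in the main study, and a site described as already treated suggests a Veteran who was treated. This is a fair inference, but no passage states it or limits the comparison to the Active arm.

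**A rule for several post-scores exists elsewhere.** Aims 1 and 2 use Maximum Cognitive Gain, or peak gain. It is a natural candidate, but Aim 5 does not invoke it, and Day 5 has a single score from which no peak can be taken.

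**Stronger readings that the documents do not support.**

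- A reader might infer that the main aims are untouched. That does not follow: MDS Maximum Cognitive Gain rests on the same 0-before, 3-after schedule.
- A reader might instead infer that Aims 1 and 2 fail. That does not follow either. Section 5.6 refers to Table 1 for how the gain is formed, and Table 1 here holds eligibility criteria, so the definition may exist but cannot be seen.
- A reader might infer that AMPS change is also uncomputable. It is not: same-day pre-scores exist on Days 2 and 3, and B4 exists for Day 5.

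**Conclusion.** The mismatch is real. As the visit lists stand, the MDS change in Aim 5 cannot be computed as defined at either site. This holds whether Aim 5 involves one optional session or two, subject to the figures not shown and the Day 1 battery not itemised.

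The AMPS outcome can be computed, but its scores are unnamed and its Day 5 pre-score may be up to 2 weeks old. The L DLPFC side is not limited to Veterans who had active stimulation there. If they were limited to that group, about 6 of 12 (or 3.5 of 7) joiners would remain, and about 3 (or 1.75) with MDS on Day 2. These counts rest on the Day 5 list being complete, on joining being unrelated to arm and, for MDS, on an assumed 6/12 split. The target of 7 is justified for the Aim 4 modelling, not for this comparison.

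Aim 5 is exploratory, so the correction is one the sponsor should make but does not decide the trial. For Aims 1 and 2 the finding is only that the starting score for MDS gain needs to be confirmed.

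**What to change.** 1. Reconcile Sections 3.0 (supplemental funding text and Aim 5), 5.3 and the Day 5 list in 5.1 on the number of optional sessions.
2. If the Day 5 list stands, state in Section 5.6 that the site comparison uses only Active-arm TBI Veterans and their Day 2 iTBS-alone session, with a paired t-test, reported with n and a 95% CI. Optional entry and Aim 4 need not change.
3. Replace the MDS change with one that the schedule supports, without adding tests to the main study: Digit Span before stimulation to the first MDS after it, both as percent correct, at both sites. The pre-score is B0 on Day 2. For Day 5 it is B4 if the days coincide, and otherwise one short Digit Span before stimulation. State that the two tests are not shown to be equivalent. State also that MDS form and site are confounded, because Section 5.5 fixes one form order for everyone and does not establish form equivalence.
4. Name the AMPS scores in advance: B0 to the first Day 2 ImE AMPS, against B4 to the Day 5 AMPS. Call this timing-matched only when Days 4 and 5 coincide; otherwise report the interval. Do not set the delayed B0-to-B1 change against the immediate Day 5 change as like for like.
5. Confirm in Section 5.6 the starting score for MDS Maximum Cognitive Gain in Aims 1 and 2, and correct the reference to Table 1.

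**Cost.** Items 1, 2, 4 and 5 are wording. Item 3 adds at most one Digit Span for up to 12 Veterans. Table 2 gives it no separate time; at an assumed 0.2 h, as for MDS, that is 12 × 0.2 = 2.4 h in total. It would be those Veterans' seventh Digit Span (screening, B0 to B4, then Day 5). The Aim 5 sample stays small, about 6 at most for each outcome. If the Day 5 list stands, L DLPFC always precedes GIMME, so practice and site cannot be separated.
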